7. REGISTRATION PROCEDURES

7.1. Pre-Registration

The purpose of preliminary registration is to allow patients likely to be eligible for the trial but where final confirmation of eligibility based on their bone marrow biopsy is pending, to be allocated a trial number for use when sending baseline tissue samples to the central laboratory (see section 10 for further details on required samples). Samples without a trial number will not be accepted by the central laboratory.

In order to undertake preliminary registration, the following criteria must be met:

- The patient must have given written informed consent for the trial
- The site investigator must have confirmed the patient is potentially eligible based on assessments performed to date

The site must then complete the preliminary registration form and send it to the UCL CTC via email, **before** sending samples to the central laboratory.

N.B. When emailing forms, patient identifiable information from the form (e.g. initials, day and month of birth) must be redacted before it is emailed to [contact]. The identifiable information must be provided to the UCL CTC via telephone so that UCL CTC can transcribe this information on to the form. The un-redacted form must then be posted to the UCL CTC, and a copy kept in the patient file at site.

Registration [contact]
Registration email address:	[contact]
UCL CTC Office hours:	09:00 to 17:00 Monday to Friday, excluding Bank Holidays

Once the UCL CTC has confirmed that the patient has been consented appropriately and is provisionally eligible for the trial, they will assign a unique trial number for the patient and email confirmation of the trial number to the main contact for the site.

This trial number will remain the patient's unique trial identifier throughout the trial, and should be used in all communications sent during the trial.

The patient must **under no circumstances** start any trial treatment until the patient has completed the full registration process (see section 7.2) and the UCL CTC have confirmed that the patient may start trial treatment.

If, after being allocated a trial number, a patient is found to be ineligible for the trial, and will not be proceeding to full registration, the site must inform the UCL CTC, quoting the patient's unique trial number and date of sample dispatch. The UCL CTC will then contact the central laboratory to request destruction of the patient's samples and will email the site to confirm destruction.

7.2. Registration

Full patient registration will be undertaken centrally at UCL CTC and this **must be performed prior to commencement of any trial treatment**. Registration evaluations should be carried out at sites as detailed in section 9.1 (Registration Assessments).

Following -registration evaluations, confirmation of eligibility and consent of a patient at a site, the registration eligibility checklist and full registration CRF form must be fully completed and emailed to UCL CTC. These will be used to confirm patient eligibility. If further information is required UCL CTC will contact the person requesting registration to discuss the patient and request updated forms to be faxed.

Once eligibility has been confirmed UCL CTC will email confirmation of the patient's inclusion in the trial to the PI, main contact and pharmacy.

Registration [contact]
Registration email address:	[contact]
UCL CTC Office hours:	09:00 to 17:00 Monday to Friday, excluding Bank Holidays

Once a patient has been fully registered onto the trial they must be provided with the following:

- A patient contact card. Site contact details for 24 hour medical care must be added to this card and patients advised to carry this with them at all times while participating in the trial

After full registration has been confirmed the PembroWM GP letter must also be completed and sent to the patient's GP.

7.3. Initial Trial Drug Supply

Merck Sharp & Dohme (MSD) Limited will provide pembrolizumab free of charge for the duration of the study for appropriately enrolled subjects.

Refer to Summary of Drug Arrangements document for details of initial supply of pembrolizumab for the trial.

Rituximab is to be supplied from Hospital Commercial Stock as detailed in the Summary of Drug Arrangements document.

8. TRIAL TREATMENT

Investigational Medicinal Products (IMPs)

For the purpose of this protocol, the IMPs are:

- Pembrolizumab (MK 3475)
- Rituximab (note: biosimilars are allowed)

Please also refer to Summary of Drug Arrangements document (SoDA) for full arrangements for the trial.

8.1. Investigational Medicinal Products

Supplied IMP

Pembrolizumab (also referred to as MK-3475) (clear to slightly opalescent, colourless to slightly yellow solution for infusion [100 mg / 4 ml vial]) is supplied free of charge by MSD Limited. Pembrolizumab is not licensed for this indication.

Please refer to the Summary of Drug Arrangements document for further details of supply, packaging and storage conditions etc.

IMP from hospital stock

Rituximab (colourless concentrate for solution for infusion [100 mg / 10 ml vial or 500 mg / 50 ml vial]) is to be provided from hospital commercial stock. Pharmacies must ensure adequate supplies for the trial. Biosimilar (e.g. Truxima) products are permitted in the trial.

Please refer to local policy and the relevant SPC for handling and storage conditions.

8.2. Treatment Summary

Patients with relapsed/refractory WM meeting the eligibility criteria will be fully registered into the study. Patients will be treated with rituximab 375mg/m² IV infusion and pembrolizumab 200mg IV infusion on a 3 weekly cycle, for a maximum of 18 cycles on the following days:

- Cycle 1:
 - Rituximab 375mg/m² - days 1, 8 and 15
 - Pembrolizumab 200mg - day 2
- Cycle 2:
 - Rituximab 375mg/m² - day 1
 - Pembrolizumab 200mg - day 1
- After cycle 2:
 - Rituximab 375mg/m² - 12 weekly on day 1 (cycles 6, 10, 14 & 18)
 - Pembrolizumab 200mg - day 1 of every cycle

Treatment will continue until cycle 18 unless disease progression or discontinuation due to toxicity or any other cause (whichever occurs sooner). Patients who experience

disease progression at any point during the trial will have the study therapy ceased and be managed as per standard of care at their institution.

Where both rituximab and pembrolizumab are delivered on the same day, rituximab should be administered first.

See diagram below for visual representation.

Cycle	1	2	3	4	5	6	7	8	9	10	11	12	13	14	15	16	17	18
Day	1	2	8	15	1	1	1	1	1	1	1	1	1	1	1	1	1	1
Rituximab (375 mg/m ² IV)	X		X	X	X			X			X			X				X
Pembrolizumab (200mg IV)		X			X	X	X	X	X	X	X	X	X	X	X	X	X	X

8.3. Trial Treatment Details

8.3.1. Criteria to receive treatment

Full blood count (FBC) and tests of renal and hepatic function should be assessed prior to every cycle (within 3 days prior to treatment) to ensure the following criteria are met:

- Neutrophils $\geq 0.5 \times 10^9/L$
- Platelets $\geq 25 \times 10^9/L$
- AST or ALT $\leq 2.5 \times ULN$
- Bilirubin $\leq 1.5 \times ULN$

If the above criteria are not met (for reasons other than disease bone marrow infiltration – see below) prior to treatment, the cycle should be delayed until the blood counts have recovered (see section 8.4 and 8.5 for information on dose delays and treatment discontinuation due to adverse events).

8.3.1.1. Patients with high levels of WM bone marrow infiltration at registration

Patients registered on to the trial with a high level of WM infiltration in the bone marrow, and neutrophils and platelets lower than $0.5 \times 10^9/L$ and $25 \times 10^9/L$ respectively, are permitted to receive treatment providing these blood counts are no lower than the level at registration. If either blood count taken prior to a treatment cycle is lower than the level at registration, the cycle should be delayed until the blood counts have recovered to the registration level. If in subsequent cycles the neutrophils and platelet counts have improved to above $0.5 \times 10^9/L$ and $25 \times 10^9/L$ respectively, these levels should be met for all future cycles of treatment, if not, treatment should be delayed.

8.3.2. Re-scheduling treatment for logistical reasons

If for logistical reasons (e.g. bank holiday), treatment cannot take place on the scheduled day, treatment days can be re-scheduled as follows:

- Doses can be brought forward a maximum of 2 days.
- Doses can be delayed for a maximum of 7 days, however, if treatment is delayed for longer than 2 days, all subsequent doses for the remainder of trial treatment should be rescheduled in line with the delayed dose. For example, if C3D1 is delayed by 3 days, C4D1 should take place 3 weeks after the delayed C3D1 date.

For dose delays as a result of adverse events please refer to section 8.4.

8.3.3. Administration for IgM flare

Prior to the first cycle, if the total IgM is >40, pre-emptive plasmapheresis is recommended to get total IgM <40 and prevent IgM flare – defined as a >25% increase in total IgM. This phenomenon has been associated with single agent rituximab therapy in this setting, and can be associated with symptomatic hyperviscosity and/or escalation of WM related symptoms (e.g. neuropathy).

See section 8.4.6 for further details on IgM flare management.

8.3.4. Pembrolizumab administration

Pembrolizumab is a potent and highly selective humanised monoclonal antibody (mAb) of the IgG4/kappa isotype designed to directly block the interaction between PD-1 and its ligands, PD-L1 and PD-L2.

The PembroWM Summary of Drug Arrangements document (SoDA) must be referred to for detailed information regarding the handling, storage, preparation and administration of pembrolizumab. A summary is outlined below:

Supply and Storage:

Pembrolizumab will be supplied in a kit containing 2 x 4mL solution for infusion vials (100mg/4ml). It should be stored in its original carton at refrigerated conditions 2 – 8 °C and protected from light.

Preparation:

Pembrolizumab infusion solutions should be prepared in 0.9% Sodium Chloride Injection or 5% Dextrose Injection and the final concentration should be between 1 mg/mL and 10 mg/mL. Please note, the preferred diluent is 0.9% Sodium Chloride and 5% dextrose is only permissible if normal saline is not available. Once diluted the product should be used as soon as possible, however storage allowances for IV bags are permitted (see SoDA for detailed information).

Administration:

Pembrolizumab should be given intravenously over 30 minutes, with a window of -5 and +10 minutes, every 3 weeks at a dose of 200mg using an infusion pump. A sterile, non-pyrogenic, low-protein binding 0.2 to 5 µm in-line filter made of polyethersulfone (PES)

or 0.2 to 5 µm add-on filter should be used when administering the product. Refer to the SoDA for the infusion materials that are compatible with pembrolizumab.

Important Information:

- Do not use pembrolizumab if discolouration is observed.
- Do not shake or freeze the vial(s) or infusion solution.
- Do not administer the product as an intravenous push or bolus.
- Unused infusion solution for injection should not be used for another infusion of the same subject or different subject.
- Do not combine, dilute or administer it as an infusion with other medicinal products or co-administer other drugs through the same infusion line.
- Contact UCL CTC immediately if there is any departure from the guidance listed in the PembroWM Summary of Drug Arrangements document.

8.3.5. Rituximab administration

Rituximab (or biosimilar equivalent) should be given intravenously at a dose of 375 mg/m² for a maximum of 1 year as indicated in the tables above. Rituximab should be administered as per local policy.

Dose banding of rituximab is allowed as per local policy. If a patient's weight changes, local policy for dose recalculation should be followed. Rapid infusion of rituximab is permitted as per local policy. For further details on the administration please refer to the SPC for details.

Patients should receive pre-medication prior to rituximab infusion as per standard local policy. Below serves as suggested guidance to the Investigator in the absence of standard local policies:

Guidance on pre-medication prior to rituximab infusion (to be given within 30 mins to 2 hours prior to treatment):

Analgesic: Paracetamol or equivalent	Antihistamine: chlorpheniramine or cetirizine equivalent	Glucocorticoid: dexamethasone, or equivalent
1000 mg orally (PO)	10 mg IV (chlorphenamine) or 10 mg PO (cetirizine)	8 mg (hydrocortisone 200 mg IV; prednisolone 50 mg)

Supportive care (e.g. G-CSF/transfusions) may be given at the discretion of the local investigator as per local practice.

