8.7. Supportive Care

Supportive Treatment

Patients should receive appropriate supportive care as deemed necessary by the treating investigator. The following supportive treatments are recommended:

- Tumour lysis syndrome medication (e.g. allopurinol*) daily for 7 days starting 24-48 hours prior to trial treatment (first cycle only)
* rasburicase can be used as per local policy
- Antiviral prophylaxis (e.g. aciclovir) for the duration of treatment and for 3 months after completion
- PCP prophylaxis: Local PCP prophylaxis policy should be followed
- Moderate anti-emetic risk: Local anti-emetic policy should be followed

Suggested supportive care measures for the management of adverse events with potential immunologic aetiology are outlined above (section 8.4). Where appropriate, these guidelines include the use of oral or intravenous treatment with corticosteroids as well as additional anti-inflammatory agents if symptoms do not improve with administration of corticosteroids. Note that several courses of steroid tapering may be necessary as symptoms may worsen when the steroid dose is decreased. For each disorder, attempts should be made to rule out other causes such infection, which might require additional supportive care. The use of corticosteroids as supportive care for any other indication, such as anti-emetic therapy, during study is not permitted (see section 8.8 below).

G-CSF/transfusions may be given prior to treatment (including during screening) at the discretion of the local investigator as per local practice.

Concomitant Medication

Concomitant medication may be given as medically indicated at the local investigator's discretion.

Viral Hepatitis

Serious or life-threatening reactivation of viral hepatitis may occur in subjects treated with rituximab. Therefore, subjects who are anti-HB core positive, or have a known history of HBV infection, should receive prophylaxis as per local policy.

Vaccines

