8.8. Contraindications

The use of topical or systemic corticosteroids or immunosuppressants should be avoided during the trial (except in the case of immune-related toxicity - see sections 8.4) because of their potential interference with the pharmacodynamic activity and efficacy of pembrolizumab. If possible, patients should stop any steroid treatment prior to study entry. If, however, this is not possible, patients will be permitted to enter the trial if the dose of steroids is at a low dose (≤ 10 mg/day prednisolone or equivalent corticosteroid) which has been stable for at least 3 months. Unless due to immune-related toxicity, the initiation of steroid treatment during the study, or the necessity to increase the dose of any ongoing steroid treatment, should lead to withdrawal of the patient from the study.

Participants are prohibited from receiving the following therapies during treatment:

- Antineoplastic systemic chemotherapy or biological therapy
- Immunotherapy not specified in this protocol
- Chemotherapy not specified in this protocol
- Investigational agents other than pembrolizumab
- Radiation therapy
 - Note: Radiation therapy to a symptomatic solitary lesion or to the brain may be allowed at the investigator's discretion.
- Live vaccines within 30 days prior to the first dose of study treatment, while participating in the study, and for 4 months after stopping treatment. Examples of live vaccines include, but are not limited to, the following: measles, mumps, rubella, varicella/zoster, yellow fever, rabies, BCG, and typhoid vaccine. Seasonal influenza vaccines for injection are generally killed virus vaccines and are allowed; however, intranasal influenza vaccines (e.g. FluMist®) are live attenuated vaccines and are not allowed.

- Systemic corticosteroids for any purpose other than to modulate symptoms from an event of clinical interest of suspected immunologic etiology. The use of physiologic doses of corticosteroids may be approved after consultation with the Sponsor.

Participants who, in the assessment by the Investigator, require the use of any of the aforementioned treatments for clinical management should be removed from the study. All treatments that the Investigator considers necessary for a participant's welfare may be administered at the discretion of the Investigator in keeping with the community standards of medical care.

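### The glucocorticoid in section 8.3.5's suggested rituximab premedication falls under the corticosteroid prohibition in sections 8.7 and 8.8, and no exception names it

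*Combined protocol and SAP*

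**What the plan says.** Three sections of the protocol bear on this.

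- **Section 8.3.5 (Rituximab administration).** The instruction is "Patients should receive pre-medication prior to rituximab infusion as per standard local policy". A table follows, introduced by "Below serves as suggested guidance to the Investigator in the absence of standard local policies". One of its three columns is headed "Glucocorticoid: dexamethasone, or equivalent", and the entry begins "8 mg (hydrocortisone 200 mg IV; prednisolone 50 mg".
- **Section 8.7 (Supportive Care).** After describing steroid treatment of adverse events with a possible immunologic cause, it states: "The use of corticosteroids as supportive care for any other indication, such as anti-emetic therapy, during study is not permitted". It refers the reader to 8.8.
- **Section 8.8 (Contraindications).** The general rule is "The use of topical or systemic corticosteroids or immunosuppressants should be avoided during the trial (except in the case of immune-related toxicity", and the reason given is that these drugs may interfere with pembrolizumab's activity and efficacy. The list of therapies prohibited during treatment includes "Systemic corticosteroids for any purpose other than to modulate symptoms from an event of clinical interest of suspected immunologic etiology". The section also says that starting steroids during the study, other than for immune-related toxicity, should lead to withdrawal of the patient.

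Section 8.3.5 does not mention the prohibition, and neither 8.7 nor 8.8 mentions premedication.

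**The concern.** Premedication before rituximab is prophylaxis against an infusion reaction. It does not treat a suspected immune event. On the wording of 8.7 and 8.8, a systemic glucocorticoid given for that purpose is a prohibited therapy, yet 8.3.5 suggests one.

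Three things are at stake:

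- **Conduct.** A site following the protocol's own fallback table would depart from 8.7 and 8.8 at the first infusion. Section 13.1 requires all protocol deviations to be notified immediately.
- **Patient status.** Read literally, the withdrawal sentence in 8.8 would apply from cycle 1 day 1. Such a patient has started treatment, so the replacement rule in 17.2.1 would not apply. If no response had been recorded and the 24-week assessment were missing, 17.2.1 would count the patient as a non-responder.
- **Interpretation.** Steroid exposure around pembrolizumab may differ between sites on a factor that 8.8 itself says could affect efficacy, while a single response rate is judged against 23 of 42.

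**Working it through.** This is mainly a comparison of texts. The plan states no figure on this point, so there is none to reproduce.

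**Step 1. Does any allowance cover rituximab premedication?**

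| Allowance | Where | Covers routine rituximab premedication? |
|---|---|---|
| Management of suspected immune-related events | 8.4.2, 8.7, 8.8 | No; premedication is prophylaxis |
| Physiologic doses after consulting the sponsor | 8.8 | Not named |
| Stable steroid at entry, at most 10 mg/day prednisolone or equivalent for at least 3 months | 8.8 | No; concerns ongoing use at entry |
| Investigator discretion for the participant's welfare | 8.8 | Not named; the preceding sentence says participants who need a prohibited therapy should be removed |
| Investigator's final decision on supportive therapy | 8.8 | Not named; continuing study treatment also needs sponsor and participant agreement |
| Corticosteroids for grade 3 or 4 pembrolizumab infusion reactions | 8.4.3 | No; treats a reaction to the other drug |
| Short prednisolone course around cycle 1 day 1 for IgM flare after stopping a BTK inhibitor | 6.2.2, criterion 25 | No; different purpose |

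None of them names it. Criterion 25 shows that where a steroid exception was wanted for another purpose, it was written down.

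**Step 2. At which infusions can the conflict arise?** The schedule is in section 8.2: rituximab on days 1, 8 and 15 of cycle 1, then on day 1 of cycles 2, 6, 10, 14 and 18, with 3-week cycles. Day 1 of cycle c is study day 1 + 21 × (c − 1), if there are no delays.

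| Infusion | Study day | Pembrolizumab |
|---|---|---|
| C1D1 | 1 | next day (C1D2) |
| C1D8 | 8 | none that day |
| C1D15 | 15 | none that day |
| C2D1 | 1 + 21 × 1 = 22 | same day |
| C6D1 | 1 + 21 × 5 = 106 | same day |
| C10D1 | 1 + 21 × 9 = 190 | same day |
| C14D1 | 1 + 21 × 13 = 274 | same day |
| C18D1 | 1 + 21 × 17 = 358 | same day |

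- Total: 3 + 1 + 4 = 8 infusions.
- Week 24 falls at 24 × 7 = 168 days after day 1, which is study day 169 (also C9D1: 1 + 21 × 8). The infusions on days 1, 8, 15, 22 and 106 precede it: 5 of the 8.
- Five of the 8 fall on a pembrolizumab day, and C1D1 is the day before the first pembrolizumab dose.

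These are maxima. They apply to a patient who completes treatment at a site that gives a steroid every time.

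**Step 3. Which sites are affected?**

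| Site's premedication practice | Consistent with 8.3.5? | Consistent with 8.7 and 8.8? |
|---|---|---|
| Local policy without a steroid | Yes | Yes |
| Local policy with a steroid | Yes | No |
| No local policy; uses the table including its glucocorticoid | Yes | No |

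The documents do not say how the 10 planned sites divide among these rows.

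**Step 4. Is the decision rule affected?** No. For X binomial with n = 42, P(X ≥ 23) is 0.0375 at a true rate of 0.40 and 0.803 at 0.60. This agrees with the stated one-sided 0.05 and 80% power, and steroid premedication does not enter the calculation.

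**The case against.** The strongest reply is that the steroid is not required. Section 8.3.5 defers to local policy, and the table is offered only where there is none. This stands. A reader might infer that no site can comply with all three sections, or that 8.8 is breached in every patient, but the documents do not support that: a site with a steroid-free policy complies throughout.

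A second reply is that 8.8 has more than one allowance and closes with investigator discretion, and that the specific section on rituximab could be read as qualifying the general prohibition. It is right that physiologic dosing is not the only allowance. But none of the allowances names premedication, and the protocol has no rule that a specific section overrides a general one. Section 8.7 also refuses another routine supportive use, anti-emesis, by name. One could add that a single pre-infusion dose is not the initiation of steroid treatment in the sense of the withdrawal sentence. The text does not say, and the prohibited-therapy bullet applies either way.

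A reader might also set the table's 50 mg prednisolone equivalent against the 10 mg/day figure used elsewhere and infer a fivefold excess. That is not like for like. The 10 mg figure in 8.8 is a level of stable daily use at entry, and in 8.4.1 and 8.5 it is a taper target after an immune-related event; the table gives a single dose. The protocol sets no limit for single-dose premedication.

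Finally, a reader might infer that the response rate will be biased. Section 8.8 speaks only of potential interference, and nothing in the documents quantifies the effect of a single premedication dose. Nor do they show that practice will in fact differ between sites. This objection stands in full.

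**Conclusion.** The inconsistency is real but conditional. The premedication that 8.3.5 suggests contains a drug class that 8.7 and 8.8 do not allow for that purpose, and no written exception resolves it. It affects sites that use the table or whose local policy includes a steroid, at up to 8 infusions per patient, 5 before the primary endpoint and the first on cycle 1 day 1. These counts assume the scheduled dosing without delay and a steroid at every infusion. The number of affected sites is unknown.

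No effect on the response rate is claimed, and the 23-of-42 rule is unaffected. The reason to act is that the protocol's own guidance, followed as written, produces a prohibited therapy and, on a literal reading, grounds for withdrawal, in a matter that 8.8 itself links to efficacy. It should be corrected.

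**What to change.** 1. The sponsor should reconcile sections 8.3.5, 8.7 and 8.8, including the withdrawal sentence in 8.8, so that they state one consistent rule on glucocorticoids before rituximab. Which rule is a clinical decision for the sponsor.
2. Sites should enter any glucocorticoid given as rituximab premedication, with dose and date, on the Rolling Concomitant Medication CRF already named in section 8.7. Concomitant medication is already reviewed before each cycle and at the response visits (9.2.1, 9.2.2), so only the explicit request is new. It should cover cycle 1 days 8 and 15, which are not cycle starts. Recording matters whichever rule is chosen, because deferring to local policy may leave practice varied between sites.
3. The statistical section should say that this exposure up to week 24 will be described alongside the response rate, by patient and by infusion, without a formal test.

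The cost is a few sentences of protocol text and entries on an existing form. No procedures, visits or patients are added.
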